3.1. SAMPLE SIZE AND POWER

The sample size for this study is based on the assumption of a treatment difference of at least 4 points in the mean change from Baseline to to endpoint in MADRS total score between

any MIN-117 dose group and placebo. A standard deviation of 9 in the change in MADRS total score from Baseline is used. Using the Bonferroni multiplicity adjustment for multiple comparisons of 2 MIN-117 dose groups with placebo and assuming an allocation of 2:1:1 for placebo and the 2 MIN-117 doses, 146 patients in the placebo group and 73 patients in each MIN-117 dose group are required to detect the treatment difference of 4 points with a power of 80% at an overall 2-sided significance level of 0.05. When adjusted for a rate of 10% of patients who will not have either Baseline or post-Baseline efficacy assessments, the required number of patients becomes 162 for the placebo group and 81 for each of the 2 MIN-117 dose groups. Therefore, the total number of patients across the 3 treatment groups will be 324.

3.2. RANDOMIZATION AND BLINDING

Central randomization will be implemented in this study. Patients will be randomized to 1 of 3 treatment arms, based on a computer-generated randomization schedule prepared by or under the supervision of Minerva before the study. The randomization will be balanced by using permuted blocks. The Interactive Web Response System (IWRS) will assign a unique treatment code, which will dictate the treatment assignment and matching study drug kit for the patient.

Approximately 324 eligible patients will be randomized in a 2:1:1 ratio to the following groups:

- Placebo
- 5.0 mg MIN-117
- 2.5 mg MIN-117

The investigator will not be provided with randomization codes. The codes will be maintained within the IWRS, which has the functionality to allow the investigator to break the blind for an individual patient, if needed.

Under normal circumstances, the blind should not be broken until all patients have completed the study and the database is locked. Otherwise, the blind should be broken only if specific emergency treatment/course of action would be dictated by knowing the treatment the patient is receiving. In such cases, the investigator may in an emergency determine the identity of the treatment by IWRS.

In the event the blind is broken, then sponsor must be informed as soon as possible. The date, time, and reason for the unblinding must be documented by the investigator in the appropriate section of the electronic case report form (eCRF), and in the source document. The documentation received from the IWRS indicating the code break must be retained with the patient's source documents in a secure manner (e.g., sealed envelope) so as not to unblind the treatment assignment to the study site, sponsor/contract research organization (CRO)

personnel. The investigator is also advised not to reveal the study treatment assignment to the study site or sponsor personnel.

3.3. HANDLING OF DATA

3.3.1. Strata and Covariates

The primary efficacy analysis and corresponding sensitivity analyses will have Baseline MADRS as a covariate. Similarly, secondary endpoints and select additional efficacy analyses will contain covariates of their respective Baseline values.

3.3.2. Examination of Patient Subsets

Select efficacy analyses will be presented by region, which will consist of the following grouping:

- US and Finland combined
- All other countries

3.3.3. Multiple Testing and Comparisons

The adjustment for multiplicity within the family of primary hypotheses will utilize the Hochberg procedure for the purpose of reporting of results. The procedure will allow the null hypothesis of no treatment difference for both the 5.0 mg and 2.5 mg doses versus placebo to be rejected if the largest p-value of comparing either of these 2 doses versus placebo is at or below 0.05. Otherwise, the lowest of these 2 p-values must be at or below 0.025 to allow for rejecting the null hypothesis for the representative dose.

The overall type I error rate for testing the 2 MIN-117 doses versus placebo for the primary and the key secondary endpoints will be controlled at the 2-sided 0.05 level. The primary family of hypotheses (corresponding to the primary endpoint) and the secondary family hypotheses (corresponding to the key secondary endpoint, the change from Baseline in HAM-A total score) will be tested in a sequential manner with suitable adjustment for multiplicity within the family of primary hypotheses and within the family of the secondary hypotheses such that a MIN-117 dose versus placebo null hypothesis contrast testing within the secondary family can be evaluated only when the same null hypothesis contrast in the primary family was rejected (the truncated Hochberg procedure).

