10.5.1. Primary Endpoint

The primary efficacy endpoint will be the change in the MADRS total score from Baseline to Week 6. This endpoint will be analyzed using MMRM with treatment arm (5.0 mg MIN-117 dose, 2.5 mg MIN-117 dose, placebo), pooled study center (by country or region based on enrollment), visit, and treatment arm-by-visit interaction as fixed effects, patient nested in treatment as random effect, and Baseline total MADRS score as covariate. An unstructured covariance matrix will be used to model the covariance of within-patient scores. The Kenward-Roger approximation ([Kenward 1997](#)) will be used to estimate denominator degrees of freedom. In this analysis in which the MMRM is fitted to all post-Baseline data, patients in the ITT analysis set who do not have complete data will still contribute to the estimates at Week 6, but will have less weight in the analysis than those patients with complete data (i.e., only the observed cases without imputation of missing values will be used in this analysis). Comparisons against placebo will be performed using the appropriate contrasts from this model at Week 6. An analysis of observed scores available at each visit will also be performed.

The adjustment for multiplicity within the family of primary hypotheses will utilize the conventional Hochberg procedure for the purpose of reporting of results. This procedure will allow the null hypothesis of no treatment difference for both the 5.0 mg and 2.5 mg doses versus placebo to be rejected if largest p-value of comparing either of these 2 doses versus placebo is at or below 0.050. Otherwise, the lowest of these 2 p-values must be at or below 0.025 to allow for rejecting the null hypothesis for the representative dose.

The overall type I error rate for testing the 2 MIN-117 doses versus placebo for the primary and the key secondary endpoint will be controlled at the 2-sided 0.05 level. The primary family of hypotheses (corresponding to the primary endpoint) and the secondary family of hypotheses (corresponding to the key secondary endpoint, the change from Baseline in HAM-A total score) will be tested in a sequential manner with suitable adjustment for multiplicity within the family of primary hypotheses and within the family of the secondary hypotheses such that a MIN-117 dose versus placebo null hypothesis contrast testing within the secondary family can be evaluated only when the same null hypothesis contrast in the primary family was rejected.

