10.5.2. Secondary and Exploratory Endpoints

The change from Baseline in CGI-S and observed CGI-I scores will be analyzed by means of an ANCOVA of ranked data, with treatment (MIN-117 doses and placebo) as a factor, and Baseline CGI-S value as a covariate.

Change from Baseline for efficacy parameters, HAM-A, IDS-SR₃₀, SHAPS, DSST, PSS, A-SEX, and sleep parameters will be analyzed using the same MMRM model and weighted combination test procedure as described above.

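### The MADRS-to-HAM-A testing rule combines untruncated Hochberg cut-offs with a dose-by-dose gate, so the promised overall 0.05 is not held and can reach about 0.095

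*SAP*

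**What the plan says.** SAP 3.3.3 sets out the scheme in four parts.

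- **MADRS cut-offs.** Both doses are declared when "the largest p-value of comparing either of these 2 doses versus placebo is at or below 0.05". Failing that, a single dose can still be declared by itself, using the usual half-alpha cut-off of 0.025 on the smaller p-value.
- **Gate.** A dose's HAM-A contrast "can be evaluated only when the same null hypothesis contrast in the primary family was rejected (the truncated Hochberg procedure".
- **HAM-A level.** No number is given. The families are tested in sequence "with suitable adjustment for multiplicity within the family of primary hypotheses and within the family of the secondary hypotheses". SAP section 5 sets a general level of 0.050 unless stated otherwise and refers back to 3.3.3.
- **Promise.** The overall type I error "for the primary and the key secondary endpoints will be controlled at the 2-sided 0.05 level".

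Protocol 10.5.1 has the same cut-offs, gate and promise but names a different procedure: "The adjustment for multiplicity within the family of primary hypotheses will utilize the conventional Hochberg procedure for the purpose of reporting of results". It does not mention truncation. Protocol 10.5.2 adds that HAM-A, with other scales, "will be analyzed using the same MMRM model and weighted combination test procedure as described above", although no such procedure is described and protocol 10.6 plans no interim analysis.

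**The concern.** Conventional Hochberg has no alpha left over while any MADRS null stands. If one dose clearly works, the other dose's MADRS null is tested at the full 0.05. If that null is true, testing the winning dose on HAM-A at any positive level pushes the total above 0.05.

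Truncated Hochberg exists to avoid this. It tightens the larger-p cut-off and releases the saved alpha to the next family. The SAP uses the name but prints the untruncated cut-off, and it gives neither a truncation fraction nor a HAM-A level. A programmer cannot derive the HAM-A threshold from the text.

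The situation is not remote. The primary hypothesis (protocol section 2) is that at least one dose beats placebo, so a single-dose win is a planned form of success. It is also the case in which a HAM-A claim has no error protection. If the missing level were chosen after unblinding, it would be a post hoc choice about a claim described as alpha-controlled.

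**Working it through.** **Inputs.** Cut-offs 0.05 and 0.025, and the dose-by-dose gate (SAP 3.3.3). Effect 4 points, SD 9, 146 placebo and 73 per dose (SAP 3.1). The within-patient MADRS/HAM-A correlation ρ is not in the documents; it is varied from 0 to 0.9.

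**Correlation of the contrasts.** The two dose contrasts share the placebo arm: (1/146)/(1/146 + 1/73) = 1/3. The MADRS contrast for one dose and the HAM-A contrast for the other therefore correlate at ρ/3.

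**Where the stated 0.05 is reproduced.** Simulating all four hypotheses gives 0.049 when every null is true, and 0.049 when both doses have a large MADRS effect and HAM-A is null.

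**Where it is not.** Take 5 mg with a large MADRS effect, 2.5 mg null on MADRS, and HAM-A null. The 5 mg gate is open, and Hochberg tests 2.5 mg on MADRS at 0.05. With HAM-A for 5 mg tested at level a and two-sided critical value c:

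P(at least one false claim) = 1 − P(|Z₁| < 1.96 and |Z₂| < c), correlation ρ/3.

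With ρ = 0 this is simple arithmetic:

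- a = 0.05: 1 − 0.95 × 0.95 = 0.0975
- a = 0.025: 1 − 0.95 × 0.975 = 0.0737
- a = 0.01: 1 − 0.95 × 0.99 = 0.0595

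With ρ = 0.9 the first two become 0.0951 and 0.0722.

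**At the planned effect.** The noncentrality is 4 / (9 × √(1/146 + 1/73)) = 4 / 1.290 = 3.10. Simulating the full procedure, with 5 mg effective on MADRS only:

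| ρ | HAM-A at 0.05 | HAM-A at 0.025 |
|---|---|---|
| 0 | 0.084 | 0.065 |
| 0.5 | 0.077 | 0.061 |
| 0.7 | 0.072 | 0.058 |
| 0.8 | 0.070 | 0.057 |

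**What truncation would require.** With fraction g below 1, the larger-p cut-off is 0.025 + 0.025g, and 0.05(1 − g)/2 passes to HAM-A when one dose wins. The printed 0.05 corresponds to g = 1, which passes 0.05 × 0 / 2 = 0.

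**The two repairs, in the same large-effect case.**

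- HAM-A opened only if both doses win on MADRS: any HAM-A claim then requires the false 2.5 mg MADRS claim first, so the total is 0.05. Simulation gives 0.050 within simulation error, and 0.046 at the planned effect.
- Truncated with g = 0.5: the larger-p cut-off is 0.025 + 0.0125 = 0.0375, and 0.05 × 0.5 / 2 = 0.0125 is passed on. With ρ = 0 the total is 1 − 0.9625 × 0.9875 = 0.0495; with ρ = 0.9 it is 0.0487. At the planned effect it is 0.045 or less.

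**The case against.** Four points can be made for the plan.

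- **The HAM-A level is not printed.** The 0.095 figure reads in the SAP's general 0.05. A reader who applies an ordinary within-family split (0.025) gets at most about 0.074. This is a fair condition on the headline figure, but the error exceeds 0.05 under either reading, and for any positive level in the large-effect limit.
- **The configuration is extreme.** Entry requires anxious distress and HAM-A of at least 18, so a dose with a large MADRS effect and no HAM-A effect is unlikely. If 5 mg works equally well on both scales and 2.5 mg does nothing, the rate is about 0.046. This limits the practical risk. It does not rescue the promise, because control over both doses and both endpoints, in its usual reading, has to cover every configuration.
- **The SAP names a valid method.** Truncated Hochberg would control the error if it were specified. The name, however, contradicts the printed 0.05 cut-off. If truncation was intended, that cut-off is wrong, and correcting it changes when both doses can be declared on MADRS.
- **The primary result is untouched.** This is true: the MADRS family alone holds 0.05, and the sample size does not depend on the gate. In a Phase 2b trial the exposure is confined to a key secondary claim.

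The weighted combination test in protocol 10.5.2 is a separate wording fault. SAP 5.2.4 specifies a plain MMRM for HAM-A, and the type I error argument does not rely on it.

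**Conclusion.** The concern holds. The printed cut-offs, the dose-by-dose gate and the promise of overall 0.05 control cannot all stand. The worst case is 0.095 to 0.0975 with HAM-A at 0.05, or 0.072 to 0.074 at 0.025. At the planned 4-point effect in one dose only, it is about 0.070 to 0.077 or 0.057 to 0.061 (ρ from 0.8 to 0.5).

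These figures rest on an assumed MADRS/HAM-A correlation, on a HAM-A level the SAP does not state, and on a normal approximation. None of these affects the direction of the result. It should be corrected before unblinding, because the plan makes an explicit error-control statement that its own rule does not meet.

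**What to change.** Choose one of the following and write it identically in SAP 3.3.3, protocol 10.5.1 and the synopsis.

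1. **Keep the MADRS cut-offs and change the gate.** Test HAM-A by Hochberg at 0.05 only if both MADRS nulls are rejected; otherwise report HAM-A p-values as nominal. Call the procedure conventional Hochberg. The cost is that no confirmatory HAM-A claim is possible when only one dose wins.
2. **Keep the dose-by-dose gate and print real truncated cut-offs.** For example, with g = 0.5: reject both MADRS nulls if the larger p is at most 0.0375, otherwise reject for the dose with the smaller p if that is at most 0.025. If one dose wins, test its HAM-A at 0.0125; if both win, test HAM-A by Hochberg at 0.05. Call it truncated Hochberg. The cost is a slightly stricter larger-p cut-off on MADRS. The value 0.5 is an illustration; the sponsor should fix g in advance.

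In either case, remove the reference to a weighted combination test from protocol 10.5.2 and the matching synopsis sentence. All of this is wording: no patients, visits or data are added.

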3.3.4. Missing Data and Outliers

Every effort will be made to obtain required data at each scheduled evaluation from all patients who have been treated. Imputation of incomplete dates is detailed in Section 3.3.5.

As part of sensitivity analyses on the primary and key secondary endpoint, patients who are missing MADRS and HAM-A scores, respectively, will have this value imputed using the

last-observation-carried-forward (LOCF) method and multiple imputation. An additional sensitivity analysis will impute scores missing due to early study discontinuation using the mean score of the placebo group. Additionally, the LOCF method may be used to impute missing MADRS and CGI-I values for the analyses of secondary and exploratory endpoints. Only post-Baseline scores will be eligible to be carried forward for this imputation. The primary analysis will use observed data without imputation.

3.3.5. Imputation of Incomplete Dates

An incomplete date is any date for which either the day, month, or year is unknown, but all three fields are not unknown. An incomplete date occurs when the exact date an event occurred or ended cannot be obtained from a patient. For many of the analyses, a complete date is necessary in order to determine if the event should be included in the analysis (i.e., if the event is treatment-emergent) or to establish the duration of an event. In such cases, incomplete dates will be imputed.

In an effort to minimize bias, the project statistician will impute dates in a systematic but reasonable manner. If the month/year is the same as the Day 1 month/year then the date will be set to the date of Day 1. In other cases, missing days will be imputed as the day component of Day 1; missing months/years will be imputed as the month/year of Day 1. If this method of imputation produces an invalid date, the last date of the month will be used.

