5.4. SAFETY ANALYSES

5.4.1. Adverse Events

Adverse events will be mapped to a Medical Dictionary for Regulatory Activities (MedDRA) version 21.0 preferred term and system organ classification. If a patient experiences multiple events that map to a single preferred term, the greatest severity grade and strongest investigator assessment of relation to study medication will be assigned to the preferred term for the appropriate summaries. Should an event have a missing severity or relationship, it will be classified as having the highest severity and/or strongest relationship to study medication.

The occurrence of TE adverse events (TEAEs) will be summarized by treatment group using preferred terms, system organ classifications, and severity. Separate summaries of TE serious adverse events (SAE), TEAE related to study treatment, TEAE leading to discontinuation of study treatment, and TE fatal adverse events will be generated. All adverse events reported will be listed for individual patients showing both verbatim and preferred terms, as well as system organ class. All adverse events that occurred prior to the

initiation of study treatment will be excluded from the tables but will be included in the listings. Any TEAE occurring after the End of Study visit will not be summarized.

Missing onset dates will be imputed as previously outlined in Section 3.3.5 as required to determine TE events. Adverse events occurring on Day 1 with missing onset times will be assumed to be TE.

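### The SAP's single partial-date rule has no cap at the End of Study visit and no end-after-onset check, so a month-only adverse-event onset in the final month is often dated after that visit

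*SAP*

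**What the plan says.** SAP 3.3.5 has one procedure for every incomplete date. It applies to starts and stops alike: "An incomplete date occurs when the exact date an event occurred or ended cannot be obtained from a patient". The stated purposes are to decide whether an event belongs in an analysis, with treatment-emergent status as the given case, and to obtain durations.

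- Day 1 month: "If the month/year is the same as the Day 1 month/year then the date will be set to the date of Day 1".
- Any other month or year: "missing days will be imputed as the day component of Day 1; missing months/years will be imputed as the month/year of Day 1".
- Fallback: "If this method of imputation produces an invalid date, the last date of the month will be used".

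SAP 5.4.1 brings this rule into the adverse-event analysis: "Missing onset dates will be imputed as previously outlined in Section 3.3.5 as required to determine TE events". The same section then sets a cut: "Any TEAE occurring after the End of Study visit will not be summarized". It does not say whether the cut is applied to recorded or imputed onsets.

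Protocol 10.8.1 has a different cut, more than 14 days after the last dose. Protocol 11.3.1 collects adverse events until the last study procedure, and serious events reported within 30 days of the last dose are also taken. SAP section 8 shows partial dates in listings as they were recorded.

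**The concern.** Giving a missing day the calendar day of Day 1 is harmless in the Day 1 month, where the event becomes treatment-emergent. It is less suitable for the month of the last visit. Routine collection stops at that visit, so an event known only to that month will usually have started on or before it. The rule can nevertheless date the event a few days later, where the 5.4.1 cut could remove it from every TEAE summary, including the serious and related ones.

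That would run against the SAP's handling of missing information elsewhere. Day 1 events without a time are taken as treatment-emergent, and a missing severity or relationship gets the highest category. Here, missing information could remove an event instead.

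Because end dates follow the same rule, an imputed end can also fall before a known onset.

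**Working it through.** **Inputs**

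- Date rule: SAP 3.3.5, applied literally.
- Last dose for a completer, Day 43: Protocol 4.3.6.
- Follow-up target, Day 57: SAP 3.3.7. Visit window of ±3 days: Time and Events Schedule, footnote a.
- Study Day = event date − Day 1 + 1: SAP 3.3.8.
- Assumption: the End of Study visit is the Visit 6 follow-up. SAP 5.4.1 does not define the term.

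**1. The plan's own figure.** 43 + 14 = 57, which matches the follow-up target. The visit is 56 days after Day 1.

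**2. The gap.** The same calendar day two months on, with the month-end fallback, is 59 to 62 days after Day 1, that is Study Day 60 to 63. The gap to a Day 57 visit is 60 − 57 = 3 to 63 − 57 = 6 days. The protocol's cut would catch these dates too: they lie 60 − 43 = 17 to 63 − 43 = 20 days after a Day 43 last dose, and the limit is 14.

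**3. How often.** I applied the rule to every Day 1 date in a four-year cycle (1,461 dates), with a month-only onset in the month of the visit.

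| Visit day | Visit in second month after Day 1 month | Imputed onset after visit | Gap where affected |
|---|---|---|---|
| 54 | 1,083 | 1,083/1,461 = 74.1% | 6-9 days |
| 57 | 1,227 | 1,227/1,461 = 84.0% | 3-6 days |
| 60 | 1,371 | 1,191/1,461 = 81.5% | 1-3 days |

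- Day 57 visit: the gap is 3 days for 162 dates, 4 for 56, 5 for 824 and 6 for 185, total 1,227. For the other 234 dates (16.0%), with Day 1 early in its month, the visit is in the next calendar month. The imputed onset then falls 25 to 28 days before the visit and the event is kept.
- Day 60 visit: for 1,371 − 1,191 = 180 dates the imputed onset falls on the visit day itself and is kept.
- Early withdrawal: assuming withdrawal evenly spread over Days 2-42 and the visit 14 days later, 52.6% are affected, by 1 to 30 days.

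**4. Examples (2018).**

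- Day 1 on 28 June: Day 43 is 9 August and the visit is 23 August. An onset in August with no day becomes 28 August (Day 62), 5 days after the visit, although 1-9 August was on treatment.
- Day 1 on 4 June: the visit is 30 July. An onset in July becomes 4 July (Day 31) and is kept.

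**5. Share of month-only onsets affected.** Assume a Day 57 visit and true onset evenly spread over Days 1-57, giving 1,461 × 57 = 83,277 combinations.

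- Imputed after the visit: 16,312/83,277 = 19.6%.
- Of those, true onset on Day 43 or earlier: 3,502/16,312 = 21.5%.
- On-treatment onsets imputed after the visit, as a share of all month-only onsets: 3,502/83,277 = 4.2%.

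**6. End dates.** Take a complete onset and an end known only to the same month. Weighting the same combinations equally, the imputed end precedes onset in 42,560/83,277 = 51.1%. For example, with Day 1 on 15 June and onset on 20 July, an end in July becomes 15 July. When the end month is later than the onset month there are no reversals.

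**7. Year only.** With Day 1 on 10 December 2017 the Day 57 visit is 4 February 2018, but an onset recorded only as 2018 becomes 10 December 2018. This needs both day and month missing and a treatment course that crosses New Year.

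**The case against.** The strongest reply is that the SAP imputes onsets only as far as treatment-emergent status requires. An onset in any month after the Day 1 month is treatment-emergent whatever its day, so on a narrow reading no date would be imputed and the cut would never see one. This stands in part. A reader might infer that the SAP deletes true TEAEs, and the text does not go that far. Nor does it rule the deletion out: 3.3.5 calls for complete dates to decide inclusion in an analysis, and a program that runs both rules in sequence drops the event.

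Other limits also stand:

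- The 84% is a share of calendar dates, not of patients or events.
- Nearly four-fifths of the onset days at risk are in off-drug follow-up.
- With clinic visits every two weeks, few onsets should lack a day.
- The rule ignores treatment arm, touches no efficacy analysis, and leaves all events in the listings.
- A reader might infer that reversed end dates corrupt reported durations. The SAP's table and figure list has no adverse-event duration output.
- A reader might infer that drugs stopped for washout in the Day 1 month will be tabulated as concomitant. SAP 5.4.3 does not cite 3.3.5, which speaks of events, and Protocol 4.3.1 asks for the date of last administration. That would follow only if the rule is extended to medications.

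**Conclusion.** The point holds as a drafting defect that should be corrected. Followed literally, 3.3.5 gives onset dates after the visit at which routine collection ends, and end dates before onset. The 3-to-6-day gap applies only to a Day 57 visit in the second calendar month after the Day 1 month; other visit days give the gaps tabulated above.

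Loss from the TEAE tables depends on the 5.4.1 cut using imputed onsets, which the SAP leaves open. The 20% figure also rests on even onset over Days 1-57 and on a missing day only. It is a share of month-only onsets, and the documents give no rate of these, so the number of events may be small. The end-date reversal is real but has no planned table to affect.

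**What to change.** Replace the single rule in SAP 3.3.5 with separate rules:

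- **Onset, day missing:** Day 1 if in the Day 1 month; for a later month, the first of that month.
- **Onset, year only:** Day 1 if that year; otherwise 1 January.
- **Limit on onset:** never later than the End of Study or last-contact date, or a known end date.
- **End:** last day of the recorded month or year, capped at last contact and never before onset.
- **Cut in 5.4.1:** an event with a partial date is excluded only if the recorded part shows that it began after the End of Study visit.
- **Medications, if 3.3.5 is used for them:** a drug recorded as stopped before Day 1 is not imputed to Day 1 or later.

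In the same enumeration, the first-of-month rule puts none of the 1,461 visit-month onsets after a visit on Day 54, 57 or 60, and the last-of-month rule gives no end before onset in the 83,277 combinations. It may keep an occasional serious event that began between the visit and the end of that month, which is the cautious direction.

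The cost is a few SAP sentences and one date macro before unblinding. No data change.
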